# 6. OBJECTIVES AND OUTCOME MEASURES

Objectives	Outcome Measures	Timepoint(s) of evaluation of this outcome measure (if applicable)
Primary Objective 1. To compare the performance of the Confirm Rx ™ ICM and Reveal LINQ ™ ICM in detecting clinically significant AF episodes (episodes longer than 6 minutes) to cardiac implantable electronic devices (CIED).	1. Confirm Rx and Reveal LINQ ™ ICM sensitivity, specificity, positive predictive value and negative predictive value will be calculated for AF episodes longer than 6 minutes	During follow-up (6 months)
Secondary Objectives		
1. To compare changes in the recording of electrograms (heart's electrical activity) R- wave amplitude from time of implant to end of follow-up (6 months)	
 
Compared the percentage of changes in R-wave amplitude between both ICMs
 
	1. During the follow- up period (6 month)
2. To compare the transmission success rate of episodes recorded by the implantable cardiac monitors to the Clinician's Web Portal.	2. The percentage of successful transmission in both ICMs will be calculated.	2. During the follow- up period (6 month)
3. To compare between both devices the number of patient-activated recordings that contains symptoms \\cts attributed to those episodes	3. The percentage of activated recordings with symptoms will be calculated.	3. During follow-up period (6 months)
Exploratory Objectives		
1. To study the changes in P-wave amplitude between different positions in the chest.	1. Percentage of change in P and R- wave amplitudes between V1 and V2 position. Percentage of change in P and R-wave amplitudes between surface	1. During implant

Trial Protocol	Version 1. 2 4 /Date: 0326/087/20234
ID-AF Study	IRAS Project number: 268739
Chief Investigator: [name]	- REC Ref: 21/LO/0508 ←
	Page 12 of 28

| |

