# 2. LAY SUMMARY

Atrial fibrillation (AF) is the most common abnormal heart rhythm disturbance, affecting 1-2 million people in the UK. The irregular heartbeat caused by AF can make the heart pump blood less efficiently. This may lead to small blood clots forming inside the heart that, if they were to breakaway, can lead to blockage of small blood vessels. As a result, AF significantly increases the risk of having a stroke, heart failure and dementia. Despite having AF, a significant proportion of people have no symptoms, and they may be only found to be in AF after having a stroke. Therefore, diagnosis largely relies on accurate ECG monitoring.

AF episodes can be unpredictable, of very short duration and easily missed unless continuous ECG monitoring is undertaken. Pacemakers can continuously record the heart's electrical activity and detect AF with a high degree of confidence. However, they are invasive and rely on electrical wires implanted inside the heart, and hence less suited to be used as primary monitoring devices. To overcome these difficulties, implantable cardiac monitors (ICM) have been designed to be placed under the skin.

The new generation of ICMs has been miniaturised and are can now be injected under the skin. Moreover, they connect with the patient's smartphone and which can used to annotate symptoms and send ECG recording to their doctor when experiencing symptoms. Previous generation of ICMs could only transmit once a day (at night) and require close proximity to a home-based stationary monitor. This resulted in frequent failed transmission and delays from arrhythmic episodes detected by ICM and transmission to their physician.

Despite these significant improvements, their ability to reliably capture AF has never been tested against pacemakers.

The aim of this project is to study the performance of the two commonly used ICMs in detecting AF episodes and explore how the new connectivity can empower patients and improve patient care. We plan to inject an ICM in 30 patients with AF and pre-existing pacemaker. After a period of 6 months, we will compare how many episodes were detected in each device. With the information collected we will try to understand the pitfalls in the current technology and develop strategies to improve it.

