# 5. BACKGROUND AND RATIONALE

Clinical significance: Atrial fibrillation (AF) is the most common sustained arrhythmia affecting millions of people worldwide, leading to significant morbidity and mortality.  It is associated with a 5-fold increase risk of ischaemic stroke, accounting for 20-25% of all strokes which are generally more severe and disabling than non-AF related strokes. In addition, patients with AF have a 3-fold increase in heart failure and 2- fold increase in dementia.

Although the exact duration of AF required to cause a thromboembolic stroke is not known, episodes longer than 6 minutes detected by a CIED have been shown to increase the risk of stroke. Significant morbidity is associated with the duration and total burden of AF. Nonetheless, a large proportion of patients remains asymptomatic despite being in AF. In pacemaker patients, only 21% reported symptoms during AF episodes that were recorded by their device. In addition, the perception of AF related symptoms may change following an AF ablation with a 2-5 fold increase in the number of asymptomatic AF episodes. Thus, symptoms alone are unreliable in identifying the presence or absence of AF. Consequently, ECG monitoring tools play a critical role in the documentation of AF.

ECG monitoring: There is a correlation between the duration and intensity of ECG monitoring and the detection of AF, with continuous long-term ECG monitoring being superior to intermittent monitoring Continuous long-term ECG monitoring can be performed either intracardiac, with cardiac implantable electronic devices (CIED), or subcutaneously, with implantable cardiac monitors (ICM).

Dual-chamber cardiac implantable electronic devices (CIED): Pacemakers, ICDs, CRTs have excellent AF diagnostic capability with high sensitivity and specificity. The atrial lead is in direct contact with the atrial myocardium and generates high quality intracardiac electrograms (EGM) that are interpreted by advanced AF algorithms. However, the invasive nature of the procedure, potentially serious long-term complications, and high cost make them an inadequate primary arrhythmia monitoring device. Yet, in patients with pre-existing CIEDs, they can be used as a 'gold-standard' AF detection monitor to validate other devices.

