First generation implantable cardiac monitors (ICM) were implanted subcutaneously, using blunt dissection, in the catherisation laboratory. Their AF detection algorithm was rudimentary, relying solely on irregular R-R intervals measurements. As a result, they were prone to false positive results caused by artefact and other irregular rhythms such as ventricular ectopy. The SMJ Confirm™ ICM had a sensitivity of 94% but a positive predictive value of only 64% for detection of clinically significant AF episodes (longer than 6 minutes). Furthermore, all ICMs transmissions to the Clinician's Web Portal required the subject to be within 2 metres of the home transmitter which resulted in suboptimal transmission success.

New generation Implantable cardiac monitors (ICM): They offer a minimally invasive approach for continuous ECG monitoring. ICMs outperform the external ambulatory ECG in the diagnosis of clinically significant arrhythmias in patients presenting with palpitations, syncope, cryptogenic stroke and post-AF ablation. . AF detection relies on a two-step approach. Firstly, they identify irregular R-R intervals and either a Markov chain model or Lorenzo plot to assign an AF probability score. Secondly, they review

the electrograms for any evidence of P waves. If no P waves are detected it is logged as AF. The two ICM to be studied are:

Reveal LINQTM ICM (MedtronicTM): Commonly used ICM with reported high sensitivity and positive predicted value. However, its AF algorithm has never been validated against CIED. Transmissions are performed through a home-monitor, 20% of which are unsuccessful I[4]. The most current version can use a smartphone app (MedtronicTM) and Bluetooth® connection to transmit the recording, however the transmission success rate has not been studied.

Confirm RxTM ICM X (AbbottTM): Was the first ICM equipped with Bluetooth® wireless technology that connects directly with the patient's smartphone via the myMerlinTM app (AbbottTM). The myMerlinTM app features include activation of ECG recordings when experiencing symptoms, viewing of transmission history to confirm successful data transfer and receiving notifications for scheduled transmission and device checks. Neither the AF algorithm nor the myMerlin App have been independently validated.

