## 8.8 Blinding

Investigators and subjects will not be blinded to investigation arm.

At the end of follow-up, the CIED and ICM electrograms catalogued by the devices as AF will be adjudicated by two electrophysiologists blinded to patient data.

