# 8.9.1 Intervention – ICM implant (Confirm Rx™ or Reveal LINQ™)

The Confirm Rx™ ICM or Reveal LINQ™ ICM will be implanted as a Day Case. Prior to implant, recording of surface electrograms will be performed in V1 and V2 position to assess P and R-wave amplitudes. The procedure will be performed under sterile conditions and local anaesthetic (lidocaine 1%) using the insertion tools supplied by the manufacturer. They have very similar implant techniques and they are both injected subcutaneously in the anterior chest wall. If there is suboptimal R wave amplitude the operator can reposition the device. The subject will be premedicated with intravenous antibiotics as per Trust Policy to reduce the risk of infection. The operator may choose to close the wound with steri-strips, glue or a suture.

At the end of the procedure the R-wave amplitude will be recorded. Subjects will be taught how to use the mobile apps or the home-based monitor, depending on the device. They will be able to initiate recordings, send transmission and record their symptoms The CIED will be programmed to record any AT/AF and save the electrogram for future adjudication. The CIED and ILR date and time clocks will be synchronized.

The Confirm Rx™ ICM and the Reveal LINQ™ ICM implant procedure is safe and minimally invasive. There are no known contraindications. Potential adverse events include bruising, haematoma, superficial infection, keloid formation, migration or extrusion.

The LINQ™ and the Confirm Rx™ only transmit recordings to their company's servers (Carelink™, for Medronic; Merlin.net™, for Abbott) via their respective smartphone app or homebased monitor. ICM recordings can only be accessed on these servers by using the clinician web portal. The assigned trial specific ID number will be used to register the device in the Carelink (for Medtronic devices) and Merlin.net (for Abbott devices); thus, no identifiable patient information will be in the servers. Access to these servers is via the clinician web portal is password protected. Transmission reports will be downloaded from the Medtronic™ and Abbott™ servers and stored in password protect excel spreadsheet that will only be used in OUH trust computers.

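### Secondary outcome 3 (share of patient-activated recordings with symptoms) mainly reflects whether the symptom entry is completed and has no rhythm term, so it cannot show whether symptoms coincide with AF

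*Combined protocol and SAP*

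**What the plan says.** The third secondary objective appears in the Synopsis (section 3) and in section 6. In section 6 it begins "To compare between both devices the number of patient-activated recordings that contains symptoms" and goes on to attribute the symptoms to episodes that it does not identify. The outcome measure is: "The percentage of activated recordings with symptoms will be calculated". The objective speaks of a number, the measure of a percentage.

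On what prompts a recording, the Lay Summary says the smartphone link can be used to "annotate symptoms and send ECG recording to their doctor when experiencing symptoms". Section 5 lists among the Confirm Rx app's features "activation of ECG recordings when experiencing symptoms". Section 8.9.1 says of trained patients: "They will be able to initiate recordings, send transmission and record their symptoms". The same section has patients taught on a mobile app or a home monitor according to the device, has the CIED store every AT/AF event with its electrogram, and has the CIED and ICM clocks aligned.

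On rhythm reading, section 8.8 states that "the CIED and ICM electrograms catalogued by the devices as AF will be adjudicated by two electrophysiologists blinded to patient data". Section 8.10.1 puts the same limit on what is downloaded for analysis. Section 7.1, in its third phase, plans adjudication of every electrogram. Section 11.2 offers only generic counts and percentages and does not mention this outcome.

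**The concern.** A percentage is informative when its numerator can vary freely within its denominator. Here the denominator is recordings that patients make because they feel something, and the numerator is those recordings in which something was felt. What remains to vary is whether the patient enters the symptom, together with accidental or test activations.

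Two things are at stake. First, a difference between the arms could come from how each system collects the entry rather than from any difference in arrhythmia symptoms. Second, a reader of the trial report is likely to take the outcome as evidence on symptomatic AF, because the trial is about AF detection and the objective speaks of attributing symptoms to episodes. Attribution needs the rhythm at that moment, and the outcome does not use it.

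**Working it through.** The plan states no size, expected value or precision for this outcome, so there is no figure to reproduce. The 327 episodes in section 11.1 belong to the primary outcome and do not bear on this one.

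**Step 1. What the outcome can vary with.** Let s be the share of activations prompted by symptoms and a the chance that a symptom is then entered. If activations without symptoms carry no entry, the expected outcome is s × a. The documents give neither s nor a. Their description of activation suggests that s is high; 0.9 to 1.0 is assumed here.

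| Assumed a | s = 0.9 | s = 1.0 |
|---|---|---|
| 1.0 | 90% | 100% |
| 0.9 | 81% | 90% |
| 0.7 | 63% | 70% |
| 0.5 | 45% | 50% |

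The range is 45% to 100%. With s near 1, nearly all the movement comes from a, the entry behaviour.

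**Step 2. What the outcome says about AF.** If a share x of activations carries a symptom, the share that is both symptomatic and in AF is at least 0 and at most x. The outcome sets no tighter bound. Illustration with assumed counts: 100 activations in one arm, 90 of them annotated.

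- 20 of the 90 during AF: outcome 90/100 = 90%; annotated recordings in AF 20/90 = 22%.
- 80 of the 90 during AF: outcome 90/100 = 90%; annotated recordings in AF 80/90 = 89%.

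The reported result is the same while the quantity of interest changes fourfold (80/20 = 4).

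**Step 3. Whether activated recordings get a rhythm reading.** Sections 8.8 and 8.10.1 limit adjudication and download to electrograms that a device catalogued as AF. On those two sections, an activated recording not so catalogued gets no reading. Section 7.1 says all electrograms are adjudicated. The documents therefore disagree. Whichever is meant, outcome 3 makes no use of the reading.

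**Step 4. Whether a rhythm-matched measure is feasible.** Outcome 3 already requires the activated recordings and their symptom entries. Section 8.9.1 supplies stored CIED AT/AF electrograms and aligned clocks, and section 8.8 supplies adjudication of those catalogued as AF. Only the time-match is missing.

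**Step 5. Rough precision of such a measure.** There are 15 patients per arm (Synopsis). Assume m annotated activations per patient and intraclass correlation ρ. The effective number per arm is 15m / (1 + (m − 1)ρ).

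- m = 2, ρ = 0.5: 30/1.5 = 20. The 95% half-width at a proportion of 50% is 1.96 × √(0.25/20) = 0.22.
- m = 10, ρ = 0.1: 150/1.9 = 78.9. The half-width is 1.96 × √(0.25/78.9) = 0.11.
- m = 10, ρ = 0.5: 150/5.5 = 27.3, so 150 recordings carry the information of about 27.

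Intervals will be wide, and ignoring clustering would make them look much narrower than they are.

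**The case against.** The strongest reply is that the objective does not name AF or rhythm. The nearest thing its unnamed episodes could refer to is the activated recordings themselves, and on that reading a percentage with symptoms entered largely does answer it. Comparing how two systems collect symptoms also fits the Lay Summary's aim of exploring how connectivity can empower patients, and section 5 notes that the Confirm Rx app lacks independent validation. This stands in part. It is a reason to keep the annotation percentage, and it means one cannot say flatly that the outcome fails its objective. It leaves the objective ambiguous, and the ambiguity needs removing.

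Three stronger readings are tempting, and the documents do not support them.

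- A reader might infer that the percentage must sit close to 100%. No activation or entry rate is given, and section 8.9.1 lists recording symptoms as an ability separate from initiating a recording. The assumed range in the working runs down to 45%.
- A reader might infer that activated recordings are never classified. Section 7.1 says otherwise, and an activation overlapping device-catalogued AF could fall under section 8.8.
- A reader might hold the outcome against the background statement in section 5 that "only 21% reported symptoms during AF episodes that were recorded by their device". That sentence is there to show that symptoms are an unreliable guide to AF. No objective or hypothesis promises a comparison with it, and it does not make clear whether it counts patients or episodes.

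The device-interface argument also has a limit. Section 8.9.1 allows an app or a home monitor depending on the device, while section 12.3 describes transmission by smartphone app for both. An interface difference is possible but not established.

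**Conclusion.** The concern holds in this form: outcome 3 is conditioned on symptom-prompted recordings, mainly reflects completion of the symptom entry, and carries no rhythm information, so it cannot show whether symptoms coincide with AF. That follows from the definition and needs no assumed rate: an observed value x is compatible with any symptomatic-AF share from 0 to x. The 90%, 22% and 89% in the example rest on invented counts and show the mechanism only. The likely value of the outcome, and the size of any interface effect, cannot be derived from the documents.

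The consequence is limited. This is the third secondary outcome, descriptive, in a 30-patient pilot. The primary accuracy measures are unaffected and no hypothesis in section 5.1 depends on it. The change is still worth making, because the information needed is nearly all planned already.

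**What to change.** 1. Keep the annotation percentage, label it a usability description, define what counts as a symptom entry, and give the counts beside it, since the objective asks for a number.
2. Add two measures by device, matched on the synchronised clocks: (a) the proportion of symptom-annotated activated recordings that coincide in time with CIED-recorded, adjudicated AF; (b) the proportion of CIED AF episodes longer than 6 minutes with a symptom recording during the episode. Measure (b) counts only symptoms that led to a recording and should be described so. The section 5 figure should not be presented as a required benchmark.
3. Summarise each measure per patient, or allow for within-patient clustering, and give intervals.
4. State in section 6 which episodes the objective means.
5. Reconcile sections 7.1, 8.8 and 8.10.1 on which electrograms are downloaded and adjudicated, and say expressly whether activated recordings are included.

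The cost is an amendment to the wording, a time-match, and a short extra analysis. No new visit or device is needed. If the reconciled text brings all activated recordings into adjudication, some added reading time follows; measures (a) and (b) need only the CIED adjudication and the recording times. Intervals will be wide where activations are few.

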# 7. STUDY DESIGN

The ID-AF study is a prospective, single centre, randomised observational study aimed at comparing the performance of the Confirm  $Rx^{M}$  and Reveal LINQM ICMs in the detection of clinically relevant atrial fibrillation (AF) episodes to cardiac implantable electronic devices (CIED)

Subjects with pre-existing cardiac implanted electronic devices (Pacemakers, CRT and ICD devices) who have remote monitoring ability and are able to record electrograms will be identified by interrogation of the John Radcliffe Hospital Pacemaker Database. Subjects with a functioning atrial lead, on remote monitoring, non-permanent AF with an AF burden of more >2% in the last year will be invited to participate. Those who have expressed an interest in participating will be invited for an initial interview (eligibility assessment, baseline assessment and informed consent).

[figure not shown]
This study will randomise 30 subjects to receive either a Confirm Rx™ ICM or a Reveal LINQ™ ICM. The ICM will be implanted in the Outpatient setting as a Day Case Procedure according to manufacturer instructions. Prior to the implant, 2 minutes of recording in V1 and V2 position with the surface ICM mapping will be performed. The R-wave amplitude will be recorded at the end of the procedure. Subjects will be taught how to use the home-based transmitter and mobile app.

As it is standard of care, the research team will book a telephone follow-up appointment at 4-6 weeks to address any questions the subjects may have regarding the ICM, review ICM battery and wound. The ICMs are programmed for automatic daily transmissions of the recorded episodes to the Clinician's Web Portal. Scheduled remote transmissions for CIED will be performed at least monthly. At 6 months, subjects will be invited to attend a Device Clinic appointment for the final download from both devices. At this time, they may choose to have the ICM removed or left in-situ but turned off. During this last visit, ICM transmissions log will be interrogated. The end of the study for each patient will be the date of the 6 months follow-up appointment.

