## 8.2. Inclusion Criteria

The participant must satisfy the following conditions:

- Participant is willing and able to give informed consent for participation in the trial.
- Male or Female aged 18 years or above.
- History of paroxysmal and persistent AF
- Dual-chamber pacemaker, ICD or CRT device with a functioning atrial lead, able to record electrograms and remote monitoring.

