## 8.3. Exclusion Criteria

The participant may not enter the trial if ANY of the following apply:

- Diagnosis of permanent AF.
- Contra-indications for implantable cardiac monitor.
- Unable to comply with the follow-up schedule.

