## 8.4. Recruitment

Potential participants with a Cardiac Implanted Electronic Devices (Pacemakers, CRT and ICD) with a functioning atrial lead will be selected in Outpatient Pacemaker Clinics, Remote Pacemaker Clinics and hospital pacemaker database by the OUH NHS Trust Cardiac Rhythm Management Team. All members of the research team are part of the Cardiac Rhythm Management Care Team. Patients will be invited to participate in the study if there is presence of high AF burden or frequent AF episodes in a device download within the last year.

A letter of invitation, a patient information brochure and a consent form will be given to potential participants at the time of the Outpatient Clinic. In the Remote Pacemaker Clinic, as potential participants are not physically present, a letter of invitation and patient information brochure will be sent by post if they have non-permanent AF in their most recent transmission. Upon receiving and considering the information participants can use the contact the Arrhythmia Research Team by email or telephone to request more information or to express their interest in being enrolled.

If they wish to participate a baseline visit will be organised which will include informed consent, screening, and eligibility assessment.

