# 8.6 Screening and Eligibility Assessment

If a subject meets the inclusion criteria they will be invited to participate in the study. The inclusion criteria are based on the pacemaker interrogation performed in clinic.

After agreeing to participate and signing the consent form, the following data will be collected:

- 1. Demographics (age, gender, ethnicity)
- 2. Detailed collection of medical history which should include atrial fibrillation history, previous cardiac procedure (cardiac surgery, atrial fibrillation ablation, direct current cardioversion), significant co-morbidities
- 3. Imaging data recorded previously as part of standard clinical practice: left ventricular systolic function, diastolic function, evidence of valvular heart disease, cardiac chamber size.
- 4. Current medications
- 5. Height, weight and BMI
- 6. Current CIED name, model, implant indication

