# **11 STATISTICS AND ANALYSIS**

## 11.1 Sample size calculation

The largest study to date using ICMs was performed in 1049 patients with known AF which were followed for 3 months. AF episodes longer than 6 minutes were seen in 53% of patients who had, on average, 7 AF episodes per month. We will recruit patients with known high frequency of AF episodes therefore we can assume AF episodes in least 40% of patients during the 6 months study period. Using the Buderer's formula, 327 episodes of AF are required if the expected AF detection algorithm sensitivity is 95% and the specificity is 85% with a 95% confidence interval. Therefore, with a rate of 7 episodes per month a minimum of 8 subjects for each ICM is needed. We will aim to recruit 30 patients so that a broad spectrum of patient characteristics can be accounted for.

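### The AF-activity entry rule is worded inconsistently and is missing from the formal criteria, so the episode yield that section 11.1 relies on is not secured

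*Combined protocol and SAP*

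**What the plan says.** The protocol describes the AF activity needed for entry in several places.

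- **Section 7 (Study Design)** has the only figure: remotely monitored subjects with "non-permanent AF with an AF burden of more >2% in the last year will be invited to participate".
- **Section 7.1 (Study Timeline)** has the database screened for patients with high burden, AF episodes, or both, and gives no figure.
- **Section 8.4 (Recruitment)** invites patients "if there is presence of high AF burden or frequent AF episodes in a device download within the last year", with neither term defined. For the remote clinic, the letter is posted "if they have non-permanent AF in their most recent transmission".
- **Section 8.2 (Inclusion Criteria)** asks only for "History of paroxysmal and persistent AF", with no burden, frequency or recency. On rhythm grounds, **section 8.3** excludes only "Diagnosis of permanent AF".
- **Section 8.6 (Screening and Eligibility Assessment)** applies the formal list: "If a subject meets the inclusion criteria they will be invited to participate in the study". It adds that these criteria rest on the pacemaker interrogation done in clinic.

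Section 11.1 (Sample size calculation) builds on a stronger premise: "We will recruit patients with known high frequency of AF episodes". It assumes AF episodes in at least 40% of patients over 6 months, takes 7 episodes per month from an earlier ICM study, states a need for 327 AF episodes, and derives a minimum of 8 subjects per ICM. The synopsis plans 15 per arm.

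**The concern.** The primary outcome (sections 6 and 11.2) is sensitivity, specificity, PPV and NPV for AF episodes longer than 6 minutes. Sensitivity and PPV can be estimated only from patients who have such episodes during follow-up. The sample size therefore depends on how many episodes the enrolled patients supply, yet no binding criterion asks for any recent AF. Staff who follow section 7 and staff who follow section 8.4 would also invite partly different patients.

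Two things are at stake. The number of episodes per arm may fall short of the figure the plan sets itself. A reader of the results also could not say which population the estimates describe.

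**Working it through.** **Inputs.** From 11.1: 327 episodes, 7 per month, at least 40% of patients with episodes, 53% in the earlier study, sensitivity 95%, specificity 85%, 95% confidence. From the synopsis: 15 per arm, 6 months. From section 7: burden above 2% in a year. Assumed: a two-sided interval (z = 1.96) and a margin of 5 points, which 11.1 does not state.

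**1. The plan's own figures.** Buderer's formula for specificity, N = z² × Sp × (1 − Sp) / [L² × (1 − prevalence)]:

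1.96² × 0.85 × 0.15 / (0.05² × 0.60) = 326.5, so 327.

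Subjects: 327 / (7 × 6) = 327 / 42 = 7.79, so 8. Both figures reproduce.

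**2. What the 8 assumes.** Dividing by 42 treats every subject as having 7 episodes a month. As 11.1 words it, that rate belongs to the 53% of patients in the earlier study who had episodes. The 40% is not carried into this step. Let f be the share of patients with 7 per month, the rest having none:

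| f | Subjects needed per ICM, 327 / (42f) | Episodes from 15, 15 × 42 × f |
|---|---|---|
| 1.00 | 8 | 630 |
| 0.53 | 15 | 334 |
| 0.40 | 20 | 252 |

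At 40%, 252 / 327 = 77%. The break-even share is 327 / 630 = 0.52, or an average of 327 / 15 = 21.8 episodes per patient in 6 months.

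**3. Whether the 2% rule secures the count.** 2% of a year is 0.02 × 365 = 7.3 days, or 175.2 hours.

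- One episode slightly longer than 7.3 days meets the rule by itself.
- Seven a month is 84 a year, so the mean duration must exceed 175.2 / 84 = 2.09 hours.
- Seven a month lasting 1 hour each is 84 / 8,760 = 0.96%. At 30 minutes it is 0.48%. Neither meets section 7, although both have the rate that 11.1 assumes and could count as frequent under 8.4.

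The rule therefore selects on time in AF and says little about episode count.

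**4. Effect on precision, episodes independent.** Wald half-width at 95% sensitivity, 1.96 × √(0.95 × 0.05 / n):

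- n = 327: 2.4 points
- n = 252: 2.7 points

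**5. Effect on precision, episodes clustered.** At f = 0.40 the 252 episodes come from 6 of 15 patients. With 42 episodes each, the design effect is 1 + 41 × ICC. The documents give no ICC, so 0.01 to 0.10 is assumed, giving 1.41 to 5.1.

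- 252 episodes act as 252 / 1.41 = 179 down to 252 / 5.1 = 49. Half-width 3.2 to 6.1 points.
- 327 episodes act as 232 down to 64. Half-width 2.8 to 5.3 points.

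The shortfall then costs about 0.4 to 0.8 points rather than 0.3. The wider end is approximate, because the Wald upper limit passes 100%.

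**The case against.** The strongest reply is that the wordings belong to two layers. Sections 7, 7.1 and 8.4 are invitation filters, and 8.2 and 8.3 are the eligibility list applied afterwards. The 2% in section 7 may be the figure behind high burden in 8.4. The 8.4 filter follows a list of all three recruitment sources, so the remote-clinic sentence may concern only how the letter is sent. Section 8.6 ties selection to device data. This is a pilot that enrols 15 per arm against a stated minimum of 8. All of this stands, and it makes a shortfall possible rather than certain. It does not define the 8.4 terms or put a threshold in 8.2.

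The 327 is also a weak benchmark for sensitivity. It comes from the specificity formula, in which only about 40% of units (131) would be AF. The sensitivity formula at the same margin gives 1.96² × 0.95 × 0.05 / (0.05² × 0.40) = 182.5, so 183 units, of which about 73 are AF. That is right, and is why the loss under independence is small. Section 11.1 nevertheless labels all 327 as AF episodes, so the plan misses its own stated target at its own floor.

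A reader might infer three stronger things that the documents do not support:

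- **The arms could fill with patients who supply almost no episodes.** This would require the invitation filters to have no effect in practice.
- **Patients with frequent short episodes are shut out.** Section 7 says who is invited, not who is barred, and 7.1 and 8.4 give these patients a route in.
- **The burden rule should go.** The synopsis and 8.1 target paroxysmal or persistent AF, and a criterion based only on episode count could exclude persistent-AF patients with few, long episodes.

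**Conclusion.** The point holds as an inconsistency with a measurable consequence. The entry wordings differ, the formal criteria carry no AF-activity requirement, and the one numeric rule does not select on the quantity that 11.1 needs. At the plan's own 40% floor, each arm yields about 252 episodes instead of 327, and the minimum is 20 subjects per ICM rather than 8. About 52% of patients must have 7 episodes a month for 15 per arm to suffice.

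These figures assume that patients outside that share contribute no episodes and that the rest have exactly 7 a month. Because 40% is stated as a floor, the true yield may be higher: at 53% the target is just met.

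The cost in precision is about 0.3 points under independence and more under clustering, for which sections 11.1 and 11.2 make no allowance. Most of the widening in step 5 comes from the clustering itself, which a better entry rule would reduce only in part. This should be corrected, but it does not undermine the trial.

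**What to change.** 1. **One criterion in 8.2.** Reconcile sections 7, 7.1, 8.2 and 8.4 into a single AF-activity criterion, and have the other sections refer to it. It should include recent CIED-logged AF episodes longer than 6 minutes over a fixed window, for example the last 6 months, so that it matches the premise of 11.1. The burden measure may stay alongside it so that persistent AF is not excluded.
2. **Remote clinic.** Treat AF in the latest transmission as a trigger to check that criterion.
3. **Section 11.1.** Restate the expected episodes and the minimum subjects per ICM with the 40% applied, or justify a higher share from the screening downloads.
4. **If recruitment has closed** (the synopsis gives 31 December 2023), report which rule admitted each patient, and the number of episodes and of contributing patients per arm.

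The cost is a protocol amendment, with approval under section 16.3 if it counts as substantial, and a somewhat narrower screening pool. Sections 8.4 and 8.6 already rely on device downloads, so little new data collection is expected. One check is needed first: section 8.9.1 sets the CIED to record all AT/AF only around ICM implant, so logs from before enrolment may be incomplete.
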